3.14.1.8 Exploratory Endpoints Analysis

The following are the analysis methods for the set of DEP exploratory endpoints. These analyses will be performed on the DEP FAS. For the dichotomous endpoints, this will be an observed-case analysis approach using the DEP FAS such that if a participant is missing the data needed to determine the endpoint, they will be considered as not having met the endpoint. For the continuous endpoint, this will be an observed-case analysis. As discussed in [Section 3.14.1.1](#), these analyses will not consider the additional blood Phe data from DEP Weekly substudy.

- **A $\geq 20\%$ reduction from baseline in blood Phe level at the third week of a participant's last 3 weeks at the iTD of SYNB1934v1**

Note that if a participant has 2 Week 3 blood Phe visits at their iTD (i.e., the participant escalated in dose then de-escalated back to their iTD) both Week 3 values will be considered such that the participant can reach the $\geq 20\%$ reduction at either of these assessments.

- **Blood Phe level $\leq 600 \mu\text{mol/L}$ at any time of the iTD of SYNB1934v1**
- **Blood Phe level $\leq 600 \mu\text{mol/L}$ at any time in the DEP**

For each of these endpoints, the number and proportion of participants meeting the corresponding criteria will be summarized along with [REDACTED]. For these endpoints using a $\leq 600 \mu\text{mol/L}$ criterion, the analysis will be performed on those participants with a baseline DEP blood Phe value $> 600 \mu\text{mol/L}$.

- ***Dose level at first blood Phe level $\leq 360 \mu\text{mol/L}$***

The distribution of the dose levels (i.e., 3×10^{11} , 6×10^{11} , 1×10^{12}) when a participant first had a blood Phe level $\leq 360 \mu\text{mol/L}$ will be summarized. The percentage will be two presented ways:

- 1) Based on the DEP FAS with a category for participants who did not reach a blood Phe level $\leq 360 \mu\text{mol/L}$
- 2) Based on the sub-set of participants who reached a blood Phe level $\leq 360 \mu\text{mol/L}$.

- ***Dose level at first $\geq 20\%$ reduction in blood Phe level***

The distribution of the dose levels (i.e., 3×10^{11} , 6×10^{11} , 1×10^{12}) when a participant first had a blood Phe reduction of level $\geq 20\%$ will be summarized. The percentage will be presented ways:

- 1) Based on the DEP FAS with a category for participants who did not reach a blood Phe level $\geq 20\%$
- 2) Based on the sub-set of participants who reached a blood Phe level $\geq 20\%$.

- ***Change in weekly blood Phe levels during each step of the dose ramp***

For the participants that participate in the DEP Weekly blood Phe substudy (see [Section 2.3.2](#)).

Summary statistics of the Weekly blood Phe, change from baseline in blood Phe, and percent change from baseline in blood Phe will be provided for each week the blood Phe is assessed.

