**DEP (Part 1):**

In the DEP, all enrolled participants will maintain a stable diet reflecting their baseline Phe intake and receive escalating doses of SYN1934v1 from approximately 3 to 15 weeks to determine an iTD, which is defined as the highest dose the participant is able to tolerate. A participant will be defined as having reached an iTD if they tolerate 3 weeks at a dose, regardless of whether other doses are tolerated.

If a participant tolerates escalation to the initial dose (Dose 1) after 3 weeks, the investigator will escalate to Dose 2. If Dose 2 is tolerated, the participant will continue on this dose for a total duration of 3 weeks prior to attempting to escalate to Dose 3. A participant will stay on his or her iTD for 3 weeks. If at any time during a 3-week dosing interval the participant or investigator considers a dose level to be intolerable, the dose may be de-escalated after discussion with the medical monitor. In this case, the participant will restart 3 weeks at the lower level iTD. After de-escalation, participants cannot escalate to a higher dose again during Part 1. In general, a dose is considered intolerable if the participant experiences Grade 3 or more severe adverse events (AEs) or Grade 2 gastrointestinal (GI) AEs that do not improve with continued dosing at the same dose level over time. If a dose is de-escalated due to a reason other than Grade 3 or greater, or Grade 2 GI AEs, or a second de-escalation is required, the medical monitor must be consulted.

Blood Phe level will be measured at each dose level after 3 weeks at that level. A responder will be defined as a participant who achieves a  $\geq 20\%$  reduction in blood Phe level compared to DEP baseline on SYN1934v1.

The DEP will contain an adaptive, seamless Phase 2b component. Once the first 20 participants have attained an iTD and completed the DEP or the 30th participant has a baseline DEP and has been in the study for 105 days, DEP data will be evaluated by an independent data monitoring committee (DMC) using a pre-specified set of criteria based on both safety and efficacy to determine whether the dose regimen is appropriate or whether any doses should be discontinued as well as whether the study should be stopped for futility.

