2.2 STUDY DESIGN

This is a 3-part, Phase 3 study consisting of a dose-escalating, open-label period (DEP; Part 1) of up to 15 weeks, followed by a 4-week, double-blind, placebo-controlled, randomized withdrawal period (RWP; Part 2), and an open-label extension (OLE; Part 3) of up to 36 months. [Figure 1](#) presents a study schematic.

In the DEP, all enrolled participants will maintain a stable diet reflecting their baseline Phe intake and receive escalating doses of SYNB1934v1 from approximately 3 to 15 weeks to determine an iTD, which is defined as the highest dose the participant is able to tolerate. A participant will be defined as having reached an iTD if they tolerate 3 weeks at a dose, regardless of whether other doses are tolerated.

Blood Phe level will be measured at each dose level after 3 weeks at that level. A responder will be defined as a participant who achieves a $\geq 20\%$ reduction in blood Phe level compared to DEP baseline on their iTD. For inclusion in the RWP primary efficacy analysis population, response will be assessed at the third week of a participant's established iTD for SYNB1934v1.

If at any time during a 3-week dosing interval in the DEP the participant or investigator considers a dose level to be intolerable, the dose may be de-escalated after discussion with the medical monitor. In this case, the participant will restart 3 weeks at the lower level iTD. After de-escalation, participants cannot escalate to a higher dose again during.

[figure not shown]
The DEP will contain an optional substudy (DEP weekly substudy) to evaluate the range and variability of [REDACTED] at each dose level. The [REDACTED] participants in this substudy will have weekly Phe and Tyr value assessments during the DEP (i.e., with Tyr assessments being primarily assessed for safety).

Once the first [REDACTED] participants have attained an iTD and completed the DEP or the [REDACTED] has a baseline DEP and has been in the study for [REDACTED], whichever occurs earlier, the DEP data will be evaluated by an independent Data Monitoring Committee (DMC). The DMC will use a pre-specified set of criteria based on both safety and efficacy to determine whether the dose regimen is appropriate or whether any doses should be discontinued as well as whether the study should be stopped for futility. Enrollment will not be paused during the interim analysis.

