3.14.1.2 Primary Efficacy Endpoint Analysis

The DEP primary efficacy endpoint is the percent change from DEP baseline in blood Phe level at the last measurement of the iTD of SYNB1934v1. The last measurement is the participant's last Week 3 blood Phe level at the iTD of SYNB1934v1.

The mean percent change from baseline at the participant's iTD will be tested by an MMRM analysis. The MMRM model will have DEP baseline blood Phe level as a fixed effect. The dependent variable is

the percent change from baseline in blood Phe level at the last measurement of the iTD of SYNB1934v1 (i.e., with duplicate blood Phe assessments being made at the last measurement).

Least-squares means for the percent change from baseline, along with the corresponding [REDACTED] confidence intervals and p-values testing a percent change from baseline equal to 0, will be calculated. The primary efficacy analysis will test the least-squares means percent change from baseline equal to 0 for the blood Phe level at the participants' last week (Week 3) at his or her established iTD.

At each of the scheduled assessments blood Phe will be drawn in duplicate. The MMRM will incorporate the participant repeated/duplicate measures. For the MMRM analysis, the results of the post-baseline duplicate samples from the Week 3 visit will be included in the statistical model (i.e., without averaging the results within a given visit before inclusion into the MMRM).

The MMRM analysis will be based on the restricted maximum likelihood method assuming an unstructured covariance structure to model the repeated-measures. A Kenward-Roger approximation will be used for the denominator degrees of freedom. If there is a convergence problem due to the unstructured covariance matrix, a variance components covariance structure will be used.

The DEP FAS will be the primary efficacy analysis population (defined in [Section 3.5](#)). As the primary efficacy analysis is considering only participants who reach an iTD (see [Section 2.5.1](#)) missing data for the DEP Week 3 blood Phe will generally be limited to those scenarios where the blood Phe sample is not analyzed. In the scenario that a participant is missing both blood Phe values at the DEP Week 3 for their iTD, the following algorithm will be applied:

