- If the participant has a corresponding previous non-missing Week 3 blood Phe value at the iTD dose (e.g., the participant escalates to a higher dose then subsequently de-escalates back to a lower dose, which is their iTD) this value will be used.
- Otherwise, the value will remain missing, and an observed-case approach will be used.

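### The exploratory DEP response endpoint in SAP 3.14.1.8 is named for the last 3 weeks at the iTD but scored at either of two iTD visits, so relative to its name the proportion can only be equal or too high

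*SAP*

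**What the plan says.** The endpoint in SAP 3.14.1.8 is a drop of at least 20%, expressed as a "reduction from baseline in blood Phe level at the third week of a participant's last 3 weeks at the iTD of SYNB1934v1". The note below it covers the person who went up a dose and came back: "if a participant has 2 Week 3 blood Phe visits at their iTD", then "both Week 3 values will be considered such that the participant can reach the" 20% threshold at either of them. The result is reported as a number and proportion of the DEP FAS. A participant missing the data needed for the endpoint counts as not having met it.

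The DEP primary endpoint treats the same person differently. In SAP 3.14.1.2, "The last measurement is the participant's last Week 3 blood Phe level at the iTD of SYNB1934v1". An earlier value is used only when both duplicates at the last visit are missing: "If the participant has a corresponding previous non-missing Week 3 blood Phe value at the iTD dose", that value is substituted.

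Two visits at one dose arise by design. The protocol synopsis says of Dose 2 that, if it is tolerated, "the participant will continue on this dose for a total duration of 3 weeks prior to attempting to escalate to Dose 3". After a de-escalation, SAP 2.2 says "the participant will restart 3 weeks at the lower level iTD". The by-dose MMRM in SAP 3.14.1.3 allows for repeat Week 3 visits at the two lower doses only.

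**The concern.** Take a participant whose Week 3 change at the middle dose is -25%, who moves up, does not tolerate the top dose, returns, and finishes the repeat 3 weeks at -10%. By the endpoint's name this participant has not met it. By the note, the participant has. In the primary analysis the same participant contributes -10%.

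The final iTD value is also the RWP baseline (SAP 3.3 and 3.14.2.1). So a participant could be counted as responding in the last 3 weeks at the iTD while entering the RWP from a value that does not show that response.

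A reader of the study report will take the proportion at its name, as response at the end of the DEP. Under the note it is response at any iTD visit, and the second chance goes only to participants who have two.

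**Working it through.** **No stated figure to reproduce.** The documents give no expected proportion, test or sample size for this endpoint. The check is therefore of direction, with an illustration of size.

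**Direction.** Let A be a qualifying value at the first iTD visit and B at the last. The name counts B; the note counts A or B.

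P(A or B) - P(B) = P(A and not B) ≥ 0

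The excess is zero if nobody has two visits, or if nobody qualifies first and then fails. Otherwise it is positive. It cannot be negative.

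**Inputs for the illustration.**
- Mean percent change -11%, SD 17%: protocol synopsis, Sample Size Considerations.
- Second scenario, single-visit rate p = 50%: borrowed from the planned responder share in the same place. That share belongs to a differently defined endpoint.
- Assumed, not in the documents: normality, the same distribution at both visits, between-visit correlation r of 0.5, 0.7 or 0.9, and a share s of participants with two iTD visits of 10%, 25% or 50%.

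**Single visit.** p = Φ((-20 + 11)/17) = Φ(-0.529) = 0.298.

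**Either visit.** P(either) = 2p - P(both), with P(both) from the bivariate normal distribution. At p = 0.298 and r = 0.5, this is 2 × 0.2983 - 0.1554 = 0.441.

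| p | r | P(both) | P(either) | Excess among those with two visits |
|---|---|---|---|---|
| 29.8% | 0.9 | 23.6% | 36.1% | 6.2 points |
| 29.8% | 0.7 | 18.9% | 40.7% | 10.9 points |
| 29.8% | 0.5 | 15.5% | 44.1% | 14.3 points |
| 50% | 0.9 | 42.8% | 57.2% | 7.2 points |
| 50% | 0.7 | 37.3% | 62.7% | 12.7 points |
| 50% | 0.5 | 33.3% | 66.7% | 16.7 points |

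**Whole cohort.** Excess = s × (P(either) - p).

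| s | p = 29.8%, r from 0.9 to 0.5 | p = 50%, r from 0.9 to 0.5 |
|---|---|---|
| 10% | 0.6 to 1.4 points | 0.7 to 1.7 points |
| 25% | 1.6 to 3.6 points | 1.8 to 4.2 points |
| 50% | 3.1 to 7.1 points | 3.6 to 8.3 points |

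As r approaches 1 the two visits always agree, and every entry goes to zero.

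**The case against.** **The note may be the intended definition.** It is explicit and prespecified, and a programmer would not be in doubt. It also fits another endpoint: protocol 8.5.1 has a 20% reduction at any time of the iTD as a key secondary, and SAP Table 1 no longer lists that among the key secondaries. The note may preserve it under a poor heading. Measured against that definition nothing is overstated. The exploratory rows of SAP Table 1 are redacted, so the formal wording cannot be checked. This stands as far as the remedy goes: renaming is as valid as rescoring. It does not remove the mismatch. SAP 3.14.1.7 and 3.14.1.8 use the any-time label for neighbouring endpoints where every iTD visit counts, and this endpoint carries a different one.

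**Multiple chances are already accepted in this plan.** The key secondary proportion in SAP 3.14.1.4 uses every Week 3 visit in the DEP. True, but its name says so.

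**Stronger readings a reader might infer.**
- *Every participant who de-escalates gets two tries.* The documents do not support this. The note applies only where two visits exist. Under SAP 2.2.2.1, a participant who de-escalates after RWP randomization leaves the study or goes to the OLE, so has no repeat DEP visit. Others may stop, or miss a sample, before the repeat Week 3.
- *The two-visit case is common.* The documents show how it arises but give no de-escalation rate.
- *The lower doses are favoured over the top dose.* Only the lower doses can have a repeat visit, but no by-iTD summary is specified for this endpoint. By-iTD analyses are planned for the primary and key secondary endpoints.
- *The RWP primary population is affected.* SAP 3.4.3 defines a responder by any time in the DEP, so this endpoint does not decide membership. SAP 2.2 describes response for that population at the third week of the established iTD, and protocol 8.2 calls the responder definition an exploratory DEP endpoint. Those passages should be reconciled, but that is a separate matter, which the change proposed here would not settle.

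**Conclusion.** The point holds as a mismatch between name and scoring rule. That the proportion cannot be too low relative to its name follows by logic and needs no assumption. That it is strictly too high needs at least one participant who qualifies at the first iTD visit and not at the last.

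The size cannot be fixed from the documents. Under the assumptions above, the excess among participants with two visits is about 6 to 14 points at the plan's mean and SD, and up to about 17 if the single-visit rate is 50%. Over both scenarios, the cohort excess is about 1 to 2 points if 10% have two visits, 2 to 4 if 25%, and 3 to 8 if 50%, and it falls to zero when the two visits always agree.

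The endpoint is exploratory and no test is described. The consequence is limited to one reported proportion and how it is read. This is a minor correction worth making before database lock.

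**What to change.** Either of two changes to SAP 3.14.1.8 would do.

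1. **Keep the name and change the note.** Suggested text: *If a participant has two Week 3 visits at the iTD, only the last (End of DEP) value is scored; the earlier value is used only if both duplicates at the last visit are missing.* This matches SAP 3.14.1.2.
2. **Keep the note and change the name** to a reduction of at least 20% at any time of the iTD, and report the last-visit proportion beside it.

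In either case, report how many participants have two iTD Week 3 visits, so that the difference can be judged.

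The cost is one sentence, plus one extra table row under the second option. No new data are needed. Under the first option the reported proportion may fall slightly.

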3.14.1.9 Subgroup Analyses

The DEP primary and key secondary efficacy analyses will be performed for the following subgroups (as defined in [Section 3.5.1](#)):

- Participants on sapropterin dihydrochloride (Kuvan) at the DEP baseline visit
- Genotypic phenotype values (GPV) subgroups.

Additionally, if a dose was discontinued (see [Section 3.17](#)) the DEP primary and key secondary efficacy endpoint analyses will be performed on the subgroup of participants who had an iTD of a discontinued dose. For the DEP primary endpoint analysis, the MMRM analysis would be performed including the participants who had an iTD corresponding to a discontinued dose(s), in addition to the participants with an iTD corresponding to the retained doses.

As a supplemental analysis, summary statistics for the following endpoints will be performed on the DEP FAS adolescent subgroup:

- Change and percent change from baseline in blood Phe level at last measurement of the iTD of SYNB1934v1.
- A $\geq 20\%$ reduction from baseline in blood Phe level at any time in the DEP

3.14.2 Part 2: RWP

The efficacy analyses for the RWP will be based on the responder RWP FAS (defined in [Section 3.5](#)) unless explicitly stated otherwise.

3.14.2.1 Primary Efficacy Endpoint Analysis

The RWP primary efficacy endpoint is the change from RWP baseline to Week 4 in blood Phe level. An MMRM analysis will be used to compare the mean change in blood Phe level between the placebo and SYNB1934v1 dose groups. The MMRM model will have treatment group, Screening Blood Phe (as a dichotomous variable: $\leq / > 720 \mu\text{mol/L}$), RWP baseline blood Phe level, iTD dose level, visit, and visit \times treatment group (interaction effect), visit \times iTD dose level (interaction effect), and visit \times RWP baseline blood Phe level (interaction effect) as fixed effects. The MMRM will also incorporate the participant's repeated measures at visits Weeks 1, 3, and 4, with visit being treated as a categorical variable. Least-squares means for both treatment groups and the SYNB1934v1 treatment group difference from placebo, along with the corresponding [REDACTED] confidence intervals and p-values will be calculated for Weeks 1, 3, and 4. The primary efficacy analysis will compare the least-squares means treatment difference between SYNB1934v1 and placebo in the change from baseline in the blood Phe level at Week 4.

At each of the scheduled assessments, blood Phe will be drawn in duplicate. The MMRM will incorporate these participant repeated measures. For the MMRM analysis, the results of each of the post-baseline duplicate samples from a visit will be included in the statistical model (i.e., without averaging the results within a given visit before inclusion into the MMRM).

The MMRM analysis will be based on the restricted maximum likelihood method. A Kenward-Roger approximation will be used for the denominator degrees of freedom. The covariance structure for the repeated-measures will be a direct product of unstructured (i.e., for the visits) and compound symmetry for the repeated assessments at a particular visit (i.e., the subject-level repeated measures has 2 dimensions, post-baseline Weeks 1, 3, and 4, as well as the 2 assessments at each visit. As such the covariance structure will use the direct product structure "UN@CS" as defined in SAS PROC Mixed).

For the dependent variable, this will be an observed-case analysis using the responder RWP FAS population, missing data will not be imputed.

In the event that a participant is missing their RWP baseline blood Phe (i.e., which is their DEP iTD Week 3 blood Phe value), the participant's last non-missing DEP Week 3 blood Phe value (i.e., the most recent non-missing Week 3 blood Phe value from a previous dose level) will be used as the RWP baseline blood Phe covariate value (i.e., as specified in [Section 3.3](#), the baseline RWP covariate value will be the mean of the corresponding duplicate blood Phe assessments). In the unlikely event that the participant does not have any non-missing DEP Week 3 blood Phe values, the blood Phe covariate value will remain missing, and the participant will be excluded from the RWP primary efficacy analysis, which is an observed case analysis. Note that the multiple imputation sensitivity analysis [Section 3.14.2.3](#) will impute missing RWP baseline blood Phe.

